--	--

	will be increased on a case-by-case basis, and liver function will be assessed twice a week until normalization of liver enzymes, and then per protocol thereafter.
Dose Escalation	
Within each cohort, treatment will be staggered so that each subsequent subject will not be infused until the preceding subject has been observed for at least 4 weeks following administration of SB-318.
 
Dose escalation to the next cohort will not occur until at least 4 weeks after the last subject in the preceding cohort has been dosed, the safety data from the prior cohort has been reviewed by the SMC, and the SMC has agreed to dose escalate.
 
Dosing and dose escalation will be paused if a Grade 3 or higher adverse event (AE) occurs, or if two Grade 2 AEs occur within the same organ class and persist for more than 2 weeks with therapy, provided these AEs are not related to the primary MPS I disease or treatment of the MPS I disease. In such an event, the SMC will be convened to assess for potential dose limiting toxicity (DLT), and to provide recommendations on whether to expand the cohort at the same dose level, to dose de-escalate, or to continue the study as planned (refer to the Stopping Rules).

Pediatric Dosing	
Pediatric dosing will not be initiated until adult safety data has been obtained and reviewed by the SMC, and only after the following conditions have been met:
 

• <math>\geq 6</math> months of safety data from 2 adults treated with SB-318 at any dose; and

• <math>\geq 4</math> weeks of safety data from 2 adults treated with SB-318 at the intended pediatric dose.

 
Younger pediatric subjects (Cohorts 6 and 7) will not be dosed until older pediatric subjects (Cohorts 4 and 5) have been dosed at the same dose level, and <math>\geq 4</math> weeks of safety data from each older subject has been reviewed by the SMC.

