During the first 20 weeks after SB-318 infusion, liver function tests (aspartate aminotransferase [AST], alanine aminotransferase [ALT], total and direct bilirubin, alkaline phosphatase, LDH, albumin, and total protein levels) will be conducted for evaluation of AAV-mediated immunogenicity twice a week. The tests may be conducted remotely. Blood samples for these tests will be drawn 2 to 4 days apart when possible, except for the first week when they will be drawn on the Day 1 and Day 7 visits. Liver function tests will subsequently be conducted at all study visits.

Previous studies with IV AAV8 FIX gene therapy have shown that liver transaminitis due to AAV immunogenicity occurs between 2 and 9 weeks after infusion, and that rapid institution of prednisone can control this immunogenicity ([Nathwani et al. 2014](#)). If in spite of the pretreatment with prednisone or equivalent corticosteroid there is evidence of transaminitis, the dose of prednisone or equivalent corticosteroid will be increased on a case-by-case basis, and liver function will be assessed twice a week until normalization of liver enzymes, and then per protocol thereafter.

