### 11.2 Dose Escalation Rules

Within each cohort, treatment will be staggered so that each subsequent subject will not be infused until the preceding subject has been observed for at least 4 weeks following administration of SB-318.

Dose escalation to the next cohort will not occur until at least 4 weeks after the last subject in the preceding cohort has been dosed, the safety data from the prior cohort has been reviewed by the SMC, and the SMC has agreed to dose escalate.

Dosing and dose escalation will be paused if a Grade 3 or higher AE occurs, or if two Grade 2 AEs occur within the same organ class and persist for more than 2 weeks with therapy, provided these AEs are not related to the primary MPS I disease or treatment of the MPS I disease. In such an event, the SMC will be convened to assess for potential dose-limiting toxicity (DLT), and to provide recommendations on whether to expand the cohort at the same dose level, to dose de-escalate, or to continue the study as planned (refer to the [Stopping Rules](#)).

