### 11.3 Pediatric Dosing

Pediatric dosing will not be initiated until adult safety data has been obtained and reviewed by the SMC, and only after the following conditions have been met:

- $\geq$ 6 months of safety data from 2 adults treated with SB-318 at any dose; and
- $\geq$ 4 weeks of safety data from 2 adults treated with SB-318 at the intended pediatric dose.

Younger pediatric subjects (Cohorts 6 and 7) may not be dosed until older pediatric subjects (Cohorts 4 and 5) have been dosed at the same dose level, and  $\geq 4$  weeks of safety data from each older subject has been reviewed by the SMC.

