#### 11.5 Study Stopping Rules

The safety data for all subjects within a cohort will be evaluated by the SMC at least 4 weeks after the last subject within that cohort was infused with SB-318. Safety data including AEs and clinical

laboratory test results (chemistry, hematology, etc.) will be evaluated to determine if it is safe to dose escalate.

Subjects in the subsequent cohort may be screened and enrolled prior to the safety review but will not be infused until the SMC has reviewed the data and approved the study for cohort escalation.

The SMC will also be convened to recommend whether the study should be stopped if any of the following criteria are met:

- Any one Grade 3 or higher AE, or any two Grade 2 AEs in the same system organ class that last more than 2 weeks with therapy, provided these AEs are not related to the primary MPS I disease or treatment of the MPS I disease.
- SAE not related to the primary MPS I disease
- Death of a subject.
- Development of a malignancy.

The study may also be stopped for any of the following reasons:

- Sangamo, in consultation with the SMC or Regulatory Agency, decides for any reason that subject safety may be compromised by continuing the study.
- Sangamo decides to discontinue development of SB-318.

If stopping criteria are met, no further dosing of subjects will be performed until a substantial amendment is submitted to the regulatory authority(ies) for review, and the amendment has been approved by the site IRB/IEC or equivalent. When no further enrolling or dosing decisions are required of the SMC, the SMC will no longer meet. Sangamo will review subject safety data on an ongoing basis.

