9.3. Pregnancy Test

Urine pregnancy test will be conducted for females of childbearing potential at Screening and Baseline, at Day 0 if >7 days from Baseline. It will be performed until Week 48 or until 3 consecutive plasma samples are negative for AAV2/6, whichever happens first. If urine pregnancy test result is positive, equivocal or impractical, a serum pregnancy test will be performed to confirm. The data will be presented in a listing.

10. Safety Monitoring Committee

An independent SMC composed of appropriate medical and scientific expertise will provide oversight of the study. For the cohort safety review, the SMC will be convened after the completion of each cohort (at least four weeks after the last subject within that cohort has received the study drug) to determine if it is safe to escalate to the next dose cohort. For the rolling safety review, the SMC will meet to review all available safety data approximately every 4-6 months after the first Cohort Safety Review. These meetings may be combined with subsequent cohort safety review meetings as appropriate.

The SMC may be convened at any time if there are excessive or unexpected toxicities associated with the conduct of the protocol. Specifically, the SMC will be convened earlier if the following occurs:

- Any two Grade 2 AEs in the same SOC that last more than 2 weeks with treatment or any one Grade 3 or greater AE, if these AEs are not related to the primary MPS I disease or treatment of the MPS I disease.
- SAEs not related to the primary MPS I disease.
- Death of a subject.
- Development of a malignancy.

Data analyses for SMC review will be presented in a separate document.

When no further enrolling or dosing decisions are required of the SMC, the SMC will no longer meet. Sangamo will continue to review subject safety data on an ongoing basis.

11. Changes to the Statistical Analysis Section of the Protocol

Secondary endpoint, change of baseline over time of dose of Aldurazyme (or equivalent ERT), will no longer be summarized.

12. References

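### Within a cohort, no rule holds the next infusion, or requires the SMC to be told, when the preceding subject has an open Grade 2 ALT/AST rise at 4 weeks

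*Protocol*

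**What the plan says.** **Stagger.** The synopsis (Dose Escalation) says that "each subsequent subject will not be infused until the preceding subject has been observed for at least 4 weeks following administration of SB-318". Section 11.2 says the same. Four weeks is a minimum, and no committee sign-off is attached to it.

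**Scheduled SMC review.** Under Section 11.5, a cohort's safety data are "evaluated by the SMC at least 4 weeks after the last subject within that cohort was infused with SB-318". SAP Section 10 adds that "the SMC will meet to review all available safety data approximately every 4-6 months after the first Cohort Safety Review". Neither review is tied to the second infusion in a cohort.

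**Pause rule.** A Grade 3 or higher AE pauses dosing at once. Dosing also pauses "if two Grade 2 AEs occur within the same organ class and persist for more than 2 weeks with therapy". Both limbs exempt events related to MPS I or its treatment.

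**Expected timing.** Section 3.5 states that "studies with IV AAV8 FIX gene therapy have shown that liver transaminitis due to AAV immunogenicity occurs between 2 and 9 weeks after infusion".

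**Milder rises.** Section 10.3 makes a Grade 1 or 2 laboratory abnormality an AE only if the investigator considers it clinically significant. Appendix 3 lets the investigator adjust or restart steroids, after consulting the Medical Monitor, when ALT exceeds twice Baseline. Section 3.5 requires twice-weekly liver tests until enzymes normalize. None of these provisions mentions the next subject.

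**The concern.** The stagger lets one subject's experience protect the next subject at the same dose. Section 12.1 acknowledges that the treatment cannot be reversed, so a warning that arrives after the next infusion cannot help that subject.

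Transaminitis heads the anticipated risks in Section 12.2. Yet the rule for moderate events has a persistence clause that, added to the earliest onset in Section 3.5, uses up the whole stagger. An investigator and Medical Monitor could be treating an open Grade 2 rise at Day 28 while the protocol permits the next infusion and does not require the SMC to hear of the event.

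**Working it through.** The plan gives no figure of its own here, so this is calendar arithmetic on its rules.

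**Inputs**
- Earliest next infusion: Day 28 of the preceding subject (synopsis; 11.2).
- Persistence needed: more than 14 days with therapy (synopsis; 11.2).
- Cited onset window: 2 to 9 weeks, Day 14 to Day 63 (3.5).
- Liver panels: Day 1 and Day 7, then twice weekly to Week 20 (3.5).

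**Step 1. When can the Grade 2 limb be met?** The rule does not say whether both events may come from one subject. Take the reading most favourable to the plan: raised ALT and raised AST in one subject count as two events, both are recorded as AEs, and therapy starts on the day of onset. The first whole day with more than 14 days elapsed is then onset + 15.

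| Onset | First day rule is met | Days after Day 28 |
|---|---|---|
| Day 14 | 14 + 15 = 29 | 1 |
| Day 21 | 21 + 15 = 36 | 8 |
| Day 28 | 28 + 15 = 43 | 15 |

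The AE listing shell in the SAP counts duration inclusively (stop minus start plus 1). On that count an onset exactly on Day 14 reaches 15 days on Day 28, the infusion day itself. The pause rule does not adopt that convention, and no later onset reaches 15 days by Day 28 under it. A single Grade 2 event never meets the rule, however long it lasts.

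**Step 2. Does another rule fill the gap?** A Grade 2 laboratory rise is below the Grade 3 limb. Unless it is serious, it does not meet the SAE trigger. The ALT step in Appendix 3 leads to a possible steroid change, and the SMC's power to meet at any time is discretionary. None of these obliges a hold or notice.

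**Step 3. Who is exposed?** Escalation to the next cohort is preceded by SMC review, so only second and later subjects within a cohort are affected.
- Cohort 3, second subject: one prior SB-318 recipient at 1.20E+14 vg/kg. Against the highest SB-913 dose in Section 8.1, the ratio is 1.20E+14 / 5.00E+13 = 2.4.
- Cohort 2, second subject: one prior SB-318 recipient at the dose, but by 08 October 2018 the SMC had reviewed SB-913 data (1.5), which Section 8.1 describes at up to 5.00E+13 vg/kg.
- Cohorts 4 to 7: Section 11.3 requires at least 4 "weeks of safety data from 2 adults treated with SB-318 at the intended pediatric dose", reviewed by the SMC. A second child in Cohorts 4 or 5 therefore follows at least 2 + 1 = 3 recipients at the dose. Cohorts 6 and 7 also wait for SMC-reviewed data from older children at the same dose.

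**Step 4. Are the data for a check already there?** Panels by Day 28: 2 (Days 1 and 7) + 2 × 3 (Weeks 2 to 4) = 8, normally 2 to 4 days apart.

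**The case against.** The strongest objection concerns timing. The 2-to-9-week window comes from AAV8 studies, for which Section 3.5 describes rapid institution of prednisone, which reads as treatment in response to a rise. Here every subject starts prednisone 2 days before infusion and, at 45 kg or more, is scheduled for 15 mg/day in Weeks 3 to 16. Tapering proceeds only if ALT/AST are stable or declining. Onset under this vector and regimen may be later, rarer or milder. Section 1.4, on clinical experience, was not in the text available for review. This stands: no frequency can be given.

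The second objection is that discretion already covers the case. Four weeks is only a minimum, the SMC may be convened at any time, steroid changes involve the Medical Monitor, and the sponsor may stop the study for safety. These controls are real, but none requires action.

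The SAP table shells carry only two dose columns, 1.00E+13 and 5.00E+13 vg/kg, so Cohort 3 may never have been dosed. The point concerns the plan as written.

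A reader might infer more than the documents support:
- **That the rule fails across the whole 2-to-9-week window.** Arithmetically it does: an onset on Day 63 matures on Day 63 + 15 = 78, which is 50 days after Day 28. But onsets on Days 29 to 63 have not begun when the next infusion falls due at the minimum interval, so no hold at that moment could act on them. They are not part of this point.
- **That the stagger itself is too short.** The documents give no onset timing for this regimen, so they do not support a longer interval.

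**Conclusion.** The gap is real but narrow. For a Grade 2 ALT/AST rise beginning at about Day 14 to 28, the pause rule can be met only 1 to 15 days after the next infusion is first permitted (for onset on Day 14, on Day 28 itself under an inclusive count). No other provision requires a hold or SMC notice.

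This rests on the 4-week minimum being used, on the AAV8 window being a fair guide, and on the preceding subject's own events. Persistent Grade 2 events in earlier subjects could trigger the rule sooner.

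It would be tempting to count all second subjects of Cohorts 2 to 7, which is 6 of the 1 + 2 × 6 = 13 base-plan infusions. That overstates the exposure: four of the six are children with SMC-reviewed adult data at their dose, and Section 3.5 makes some cohorts conditional. The case that matters most is the second subject of Cohort 3; Cohort 2 matters less. Nor does the text support saying that severe toxicity could pass unnoticed. A Grade 3 or higher AE pauses dosing, and an SAE not related to MPS I convenes the SMC.

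The change is a cheap improvement, not a correction of a serious fault.

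**What to change.** Keep the 4-week minimum. Add to Section 11.2 and to the synopsis Dose Escalation text:

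> Before the next subject in a cohort starts prednisone (Day -2), the latest liver panel of the preceding subject(s) in that cohort will be checked. If a Grade 2 ALT or AST elevation (CTCAE 4.03, onset after SB-318, not attributed to MPS I or its treatment, whether or not recorded as an AE) is ongoing, the infusion is held until it falls below Grade 2, or until it has been reported to the SMC and the SMC agrees to proceed. Grade 3 or higher elevations remain governed by the existing pause and stopping rules in 11.2, 11.5 and 12.3. Baseline liver biopsy and lumbar puncture need not be repeated because of such a hold.

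Place it in 11.2 rather than among the stopping criteria, because Section 11.5 says: "If stopping criteria are met, no further dosing of subjects will be performed until a substantial amendment is submitted".

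**Cost.** No new sampling from the preceding subject. Checking before prednisone starts spares the waiting subject needless steroid exposure. Some infusions will be delayed, with occasional ad hoc SMC contact. Non-invasive baseline tests may need repeating if the 21-day window in Section 6.3 lapses, and ERT may need rescheduling. SMC response time is not stated; if it agrees within 3 to 14 days (an assumption), the delay is at most that long from the due date.

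**Limit.** At the minimum interval the check falls no later than the preceding subject's Day 28 − 2 = 26, so a rise first seen in the last days before infusion could be missed.

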## ABBREVIATIONS

AAV	adeno-associated virus
AAV2/6	adeno-associated virus serotype 2/6
ACTH	adrenocorticotropic hormone
AE	adverse event/experience
AFP	$\alpha$ -fetoprotein
ALT	alanine aminotransferase (SGPT)
ANOVA	analysis-of-variance
AR	adverse reaction
AST	aspartate aminotransferase (SGOT)
BSC	BioSafety Committee
BSID-III	Bayley Scales of Infant Development
CNS	central nervous system
CRF	case report form
CSF	cerebrospinal fluid
CTCAE	Common Terminology Criteria for Adverse Events
DLT	dose-limiting toxicity
DNA	deoxyribonucleic acid
DS	dermatan sulfate
DSB	double strand break
ECG	electrocardiogram
ECHO	echocardiogram
eCRF	electronic CRF
ELISA	enzyme linked immunoassay
EOS	End of Study
ERT	enzyme replacement therapy
ETV	early termination visit
FDA	Food and Drug Administration
FIX	Factor IX
FSHD	facioscapulohumeral muscular dystrophy
GAG	glycosaminoglycan
HBV	hepatitis B virus
HCC	hepato-cellular carcinoma
HCV	hepatitis C virus
HDR	homology-directed repair
HEENT	head, eyes, ears, nose, and throat
hFIX	human Factor IX
HIV	human immunodeficiency virus
hIDUA	human IDUA
HS	heparan sulfate
HSCT	hematopoietic stem cell transplantation
IAR	infusion-associated reaction
IATA	International Air Transport Association
ICH	International Council for Harmonisation
IDUA	iduronidase
IEC	institutional ethics committee

iPSC	induced pluripotent stem cells
IRB	institutional review board
ITR	inverted terminal repeat
IV	intravenous
JROM	joint range of motion
LDH	lactate dehydrogenase
LTFU	long-term follow-up
MedDRA	Medical Dictionary for Regulatory Activities
MHRA	Medicines and Healthcare Products Regulatory Agency
MPS I	Mucopolysaccharidosis I
MPS IH	Hurler syndromeg
MPS IHS	Hurler-Scheie syndrome
MPS IS	Scheie syndrome
MRI	magnetic resonance imaging
mRNA	messenger RNA
NHEJ	non-homologous end-joining
NIH	National Institutes of Health
OHR	Office for Human Research
PBS	phosphate buffered saline
PCR	polymerase chain reaction
PFT	pulmonary function test
rAAV	recombinant AAV
rAAV2/6	recombinant AAV2/6
RNA	ribonucleic acid
RSI	reference safety information
SAE	serious adverse event
SMC	Safety Monitoring Committee
SMCHD1	structural maintenance of chromosomes flexible hinge domain containing 1
SNP	single-nucleotide polymorphism
SUSAR	suspected unexpected serious adverse reaction
TEAE	treatment-emergent AE
ULN	upper limit of normal
VABS-II	Vineland Adaptive Behavior Scales
vg	viral genomes
WASI-II	Wechsler Abbreviated Scale of Intelligence, Second Edition ( Shapiro et al. 2015 )
WPPSI-IV	Wechsler Preschool and Primary Scale of Intelligence
ZFN	zinc finger nuclease
ZFP	zinc finger protein
6MWT	6-minute walk test

## 1 INTRODUCTION

### 1.1 Mucopolysaccharidosis I

Mucopolysaccharidosis type I (MPS I), also referred to as Hurler (MPS IH)/Hurler-Scheie (MPS HIS)/Scheie (MPS IS) syndrome, is a recessive lysosomal storage disorder. According to the National Institute of Neurological Disorders and Stroke (NINDS) factsheet for MPS I, the estimated incidence is 1 in about 100,000 births for severe MPS I, 1 in about 500,000 births for attenuated MPS I, and 1 in about 115,000 births for disease that falls between severe and attenuated.

MPS I is associated with mutations in the gene encoding the iduronidase (IDUA) enzyme, which degrades glycosaminoglycans (sulfated carbohydrate polymers; GAGs). Mutations in the IDUA gene diminish or eliminate IDUA enzyme activity, which results in the accumulation of toxic GAGs in urine and body tissues.

Depending on the specific type of IDUA mutation (more than 100 different mutations have been described) and the levels of the resulting residual IDUA enzyme activity, patients will develop either the severe MPS IH or the attenuated variants MPS IHS and MPS IS. It has been estimated that 50-80% of all MPS I patients present with the severe form of the disease ([Muenzer et al. 2009](#)). MPS IH patients show symptoms of developmental delay before the end of their first year of life, as well as halted growth and progressive mental decline between ages 2-4 years. Other symptoms include organomegaly, corneal clouding, joint stiffness, skeletal deformities (including abnormal spinal bones), coarse facial features with enlarged tongue, hearing loss, and hernias. The life expectancy of MPS IH patients is less than 10 years.

Patients with the attenuated forms of the disease share most of these clinical manifestations but with less severe symptoms. In addition, there is no central nervous system (CNS) involvement, and therefore MPS IHS and MPS IS patients do not suffer from mental retardation. Many of these patients can survive into adulthood but with significant morbidity.

Current therapies for MPS I include hematopoietic stem cell transplantation (HSCT; using bone marrow or umbilical cord stem cells) and enzyme replacement therapy (ERT; using a polymorphic recombinant protein produced in Chinese Hamster Ovary cells, Aldurazyme).

Almost all patients with MPS IH undergo HSCT. If patients are diagnosed early (at <2.5 years), therapeutic intervention by HSCT can prevent or reverse most clinical features including the neurocognitive symptoms. Unfortunately, the mortality rate after HSCT has been reported to be 15%, and survival rate with successful engraftment is 56%, although recent improvements in HSCT procedure have improved overall outcomes ([Boelens et al. 2013](#)).

ERT has been shown to improve pulmonary function, hepatosplenomegaly, and exercise capacity, and to lead to improved health-related quality of life. ERT should be instituted as early as possible. However, drawbacks of ERT include the need for life-long treatment; development of neutralizing antibodies; inability to cross the blood brain barrier; continued cardiac, orthopedic, and ocular complications; and the inconvenience of weekly intravenous (IV) infusions. These drawbacks underscore the urgent need to develop a broader array of curative therapies for MPS I.

The objective and rationale for the proposed SB-318 investigational therapy is to abrogate or decrease the need for ERT using *in vivo* genome editing. The proposed treatment employs recombinant adeno-associated virus (rAAV) comprising engineered zinc finger nucleases (ZFNs) to site-specifically integrate a corrective copy of the human iduronidase enzyme (IDUA)

[figure not shown]
transgene into the genome of subjects' own hepatocytes *in vivo*. Integration of the hIDUA transgene is targeted to intron 1 of the albumin locus, resulting in stable, high level, liver-specific expression and secretion of hIDUA into the blood. Placement of the hIDUA transgene under the control of the highly expressed endogenous albumin locus is expected to provide permanent, liver-specific expression of hIDUA for the lifetime of an MPS I patient.

